### 9.6.7. Response Rate

Response rate at 3 months post RF ablation is defined in Table 9-3. Complete Response (CR) and Partial Response (PR) will be considered as treatment response. Pain Progression (PP) and Indeterminate Response (IR) will be considered as treatment non-response.

T	able	9-3:	Co	mposite Er	ndpoint
,	_				4.1

ient nse	Complete Response (CR)	A worst pain score of 0 with no concomitant increase in daily oral morphine equivalent dose (OMED) within the last 24 hours
Treatment Response	Partial Response (PR)	Pain reduction of 2 or more on a scale of 0-10 without increase in OMED, or OMED reduction of 25% in the last 24 hours or more from baseline without an increase in pain.
Treatment Non- response	Pain Progression (PP)	Increase in pain score of 2 or more above baseline worst pain score with stable OMED, or an increase of 25% or more in OMED within the last 24 hours compared with baseline with the worst pain score stable or 1 point above baseline.
Treat	Indeterminate Response (IR)	Any response that is not captured by the complete response, partial response, or pain progression definitions

#### 9.6.8.

#MDT16075 Version 4.0 Page 39 of 81

### 9.7. Assessment of Quality of Life Measures

Subjects and/or Principal Investigator or qualified (delegated) designee (if completed by phone) will complete the study questionnaires confidentially on paper forms and this data will be entered into the OC RDC system by site personnel. The patient can consult with the site for direction on how to complete the questionnaires. Questionnaires should be completed prior to the meeting with the investigator. Site personnel should review all forms for completeness.

### 9.7.9. European Quality of Life – Five Dimensions (EQ-5D-5L)

The European Quality of Life – Five Dimensions (EQ-5D), version 5L, is a standardized measure of health status developed by the EuroQol Group and a widely used validated tool to determine health-related quality of life. The EQ-5D-5L consists of two sections, the descriptive system and the EQ visual analogue scale (EQ VAS).

The EQ-5D descriptive system consists of 5 dimensions: mobility, self-care, usual activities, pain/discomfort, and anxiety/depression. Each dimension has 5 levels of severity: no problems, slight problems, moderate problems, severe problems, extreme problems. The subjects are asked to indicate his/her health state by selecting the most appropriate statement in each of the 5 dimensions.

The EQ VAS records the respondent's self-rated health on a 20 cm vertical, visual analogue scale with endpoints labelled 'the best health you can imagine' and 'the worst health you can imagine'. This information can be used as a quantitative measure of health as judged by the individual respondents.

The EQ-5D can be completed by the subject, in-person interview, or by phone interview by the Principal Investigator or qualified (delegated) designee.

#### 9.7.10. European Organization for Research and Treatment (EORTC QLQ-C15-PAL) 35

The EORTC QLQ-C15-PAL is a module developed to measure the QOL in patients with bone metastases. It includes four subscales: painful sites, pain characteristics, functional interference, and psychosocial aspects. This questionnaire is not applicable for subjects with benign bone tumors.

The EORTC QLQ-C15-PAL must be completed by the subject.

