#### 9.6.4. Disease Characteristics

- Primary cancer type and year of diagnosis
- Histology (if available)
- Metastases and/or tumor site information location, characteristics
- Imaging (if available), for US and CAN subject/sites only

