#### 9.6.6. Prior and Concomitant Medications

There are no restrictions to prior or concomitant medications before or during the study. The specific concomitant medications listed below should be documented as concomitant medications and will be updated at each visit:

- **Osteoporosis medication(s):** Antiresorptive medications (e.g., bisphosphonates, parathyroid hormone (PTH), calcitonin), calcium, and vitamin D.
- **Steroid(s):** any steroid use, including steroid inhalers
- **Oral narcotics in last 24 hours.** This information will be converted to oral morphine equivalent dose (OMED) (including transdermal patches)

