#### 13.3.5. Sample Size Methods and Assumptions

The standard deviation of change from Greenwood et al (2015) is estimated to be 4.1 at 4 weeks. The standard deviation of change in the CAFE study Berenson et al (2011) was 3.2 at 1 month. The standard deviation of change from Lane et al (2011) is estimated to be 2.4 at 1 day post-procedure. It is not known which of those studies will most closely match the population and test conditions in this study. The median of those 3 studies is 3.2. To account for this study having a longer follow-up period and a more diverse patient population, and thus more opportunity for variability, the standard deviation for our sample size calculation will be increased to 3.5.

The minimal clinically important difference (MCID) of 2 points was used to interpret pain score differences in terms of clinical relevance in Bagla et al (2016) and a clinically significant change in pain of 2 points was also identified in Greenwood. This will be used for our calculations.

Bagla followed subjects for 3 months post procedure. They reported that pain scores were provided for 68% of subjects (32% not provided) at 3 months. This will be used for our calculations.

The PASS program used to calculate the sample size was the one-sample t-test power analysis, mean0=0, meanA=2, standard deviation (of change) =3.5, two-sided significance level (alpha)=0.05, and power=0.90. The required sample size was 35. To account for subjects getting treated but not providing the 3-Month data, the treated sample size is adjusted for a 32% loss, to 52.

#MDT16075 Version 4.0

Page 58 of 81

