### 7.4 Handling of Missing, Unused, and Spurious Data and Dropouts

The primary and secondary objective endpoint assessments are planned to be collected at the 3-Month follow-up visit.

Imputation of values for missing data for primary and secondary efficacy analyses will be performed as follows.

Completers Analysis Set: The Completers Analysis Set will be analyzed without imputations for missing data. (By definition, the endpoint data was provided.) Based on published data in this patient population (Bagla, 2016) it is assumed that the primary reasons for missing endpoint data will be death or inability to contact subjects due to deteriorating health and not related to pain score level. Thus, inclusion in the Completers Analysis Set is assumed to not be confounded with endpoint pain score level.

Sensitivity Analysis: The Treated Analysis Set is expected to have missing endpoint data. The frequency, timing, and reasons for missing data will be reported and analyzed to assess potential for bias. Sensitivity analyses of the primary objective, detailed in the primary objective Analysis Methods section below, will include analyzing the Treated Analysis Set using multiple imputation and single imputation.

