#### **Analysis Methods**

Revision 1.0

Page 11 of 15

The main analysis for the primary objective hypothesis testing will be on the Primary Objective Cohort using the Completers Analysis Set.

A two-sided t-test with alpha=0.05 will be used to test the null hypothesis of no change in worst-pain score between baseline and 3 months. If the p-value is <0.05, the primary objective will be demonstrated, and statistical significance will be declared.

If the distribution of the change scores does not meet the assumption of normality, by calculating the Shapiro-Wilk W statistic probability, the non-parametric Wilcoxon signed-rank test will be used to test for significant change with alpha=0.05, two-sided. P-values less than 0.05 for the Shapiro-Wilk statistic will indicate non-normality.

In order to include all the treated subjects in the analysis, a sensitivity analysis will be performed on the Treated Analysis Set. The endpoint data will first undergo multiple imputations (MI). Rather than filling in a single value for each missing value, MI replaces each missing value with a set of "plausible" values that represent the uncertainty about the correct value to impute. These multiple imputed datasets are then analyzed using standard statistical procedures and then combined into one analysis result with an appropriately increased variance. The model variables in the MI analysis may include the following when deemed appropriate: the endpoint variable at 3 months and the endpoint variable at baseline, 3 days, 1 week, and 1 month, baseline covariates of subject age, Karnofsky score, and time from primary cancer diagnosis to baseline. The method to be used is the Markov chain Monte Carlo (MCMC) method of SAS (version 9.4 or higher). This is an iterative method that can be used when the pattern of missing data is arbitrary (monotone or non-monotone). The default number of iterations will be used (n=25) and, if needed, will be increased until the Markov chain converges. The seed will be "16075".

To allow comparison to Bagla (2016) results, a single imputation method, Last Observation Carried Forward, will also be performed, substituting the Treated Analysis Set's endpoint variable at the last available follow-up for the missing endpoint variable.

The analyses above are for the Primary Objective Report. For the Final Study Report, descriptive statistics, as well as confidence intervals, of the change in pain will be reported.

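### The multiple-imputation check on the completers-only result names no post-ablation measure of health or opioid use, although the plan blames deteriorating health for missing scores and collects both at every early visit

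*Combined protocol and SAP*

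**What the plan says.** The primary test is a one-sample t-test on completers without imputation (SAP 7.4 and 7.9.1; CIP 13.1.4 and 13.3.6). SAP 7.4 gives the expected cause of loss: "primary reasons for missing endpoint data will be death or inability to contact subjects due to deteriorating health". Both documents then assume that this is unrelated to pain level.

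Two sensitivity analyses use the Treated set. One is last observation carried forward, which the SAP includes for comparison with an earlier series. The other is multiple imputation by MCMC. SAP 7.9.1 introduces its variables permissively, as ones that may be used where suitable: worst pain at baseline, 3 days, 1 week, 1 month and 3 months, and "baseline covariates of subject age, Karnofsky score, and time from primary cancer diagnosis to baseline". CIP 13.3.6 lists the same pain scores, adds unscheduled visits, and refers to baseline covariates without naming them.

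Karnofsky is scheduled at baseline only, which may be up to 21 days before ablation (CIP Table 9-1). For diagnosis date, CIP 9.6.4 collects "Primary cancer type and year of diagnosis". EQ-5D-5L, which contains the EQ VAS, is taken at baseline and at each follow-up visit (CIP 9.1.2 and 9.1.5). CIP 9.7.9 says of the EQ VAS: "This information can be used as a quantitative measure of health as judged by the individual respondents". Oral narcotic intake over 24 hours is recorded at the same visits and converted to oral morphine equivalent dose, OMED (CIP 9.6.6). Both can also be obtained by phone (CIP 9.9). Neither appears in either imputation list.

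**The concern.** Multiple imputation is valid here only if, given the variables in the model, missingness carries no further information about 3-month pain. The plan names a driver of missingness and measures it repeatedly after ablation, then leaves it out of the model meant to test the completers-only assumption. Early pain scores capture only the part of declining health that already shows as pain. Opioid dose matters for a related reason: two subjects with the same 1-month pain score on very different doses may not have the same outlook at 3 months.

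If the omitted information matters, the imputed result carries some of the same bias as the completers. Agreement between the two would then look like confirmation when it is partly a shared error.

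**Working it through.** **1. The plan's own figures.** Inputs from CIP 13.3.5: a 2-point difference, "standard deviation (of change) =3.5, two-sided significance level (alpha)=0.05, and power=0.90", and 32% loss. The noncentrality at n = 35 is (2/3.5) × √35 = 3.38. Two-sided power from the noncentral t is 0.907 at n = 35 and 0.899 at n = 34, so "The required sample size was 35" reproduces. 35/(1 − 0.32) = 51.5, rounded up to 52 treated, which leaves 52 − 35 = 17 missing. These figures are not in dispute.

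**2. The variables side by side.**

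| Variable | Measured after ablation, before 3 months | Named for imputation |
|---|---|---|
| Worst pain | 3 days, 1 week, 1 month | Yes |
| Age | No | Yes (SAP) |
| Karnofsky | No | Yes (SAP) |
| Time from diagnosis | No; year only | Yes (SAP) |
| EQ VAS | 3 days, 1 week, 1 month | No |
| OMED | 3 days, 1 week, 1 month | No |

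**3. Size of the possible bias.** Bias in the mean = fraction missing × (mean imputed score − mean true score among the missing). It was simulated with 400,000 subjects per scenario, the outcome scaled to SD 3.5 and 32% missing. Missingness was logistic in a 1-month health score H (higher is worse), and 3-month pain was imputed by regression on 1-month pain, with and without H.

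Assumptions, none from the documents: correlation ρ of 1-month with 3-month pain 0.5 or 0.7; correlation of H with 1-month pain 0.4; partial correlation π of H with 3-month pain given 1-month pain from −0.3 to 0.5; odds ratio for missingness 2 or 3 per SD of H. Negative bias means too much apparent improvement. Ranges cover both values of ρ and both odds ratios.

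| π | Completers | Imputation without H | Imputed values themselves |
|---|---|---|---|
| 0 | −0.15 to −0.29 | 0.00 | about 0 |
| 0.2 | −0.26 to −0.41 | −0.09 to −0.17 | −0.30 to −0.52 |
| 0.3 | −0.31 to −0.48 | −0.14 to −0.25 | −0.44 to −0.77 |
| 0.5 | −0.42 to −0.61 | −0.23 to −0.41 | −0.73 to −1.26 |
| −0.3 | −0.09 to +0.03 | +0.14 to +0.24 | +0.44 to +0.74 |

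Example: 0.32 × (−0.77) = −0.25. At an odds ratio of 1 all biases are about 0. With H in the model, bias is within 0.01 throughout.

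**4. Which rows are credible.** The implied correlation of 1-month health with 3-month pain is 0.4ρ + π√((1 − ρ²)(1 − 0.4²)).

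- For ρ = 0.5 this is 0.20 + 0.794π; for ρ = 0.7 it is 0.28 + 0.655π.
- π = 0.2 gives 0.36 and 0.41, close to the same-visit value of 0.4.
- π = 0.3 gives 0.44 and 0.48.
- π = 0.5 gives 0.60 and 0.61, so health would have to predict pain two months later much better than it tracks pain at the same visit. That row is an upper extreme.

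Setting it aside, the overstatement runs from 0 to about 0.25 points.

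**5. Trial-sized check.** A simulation at N = 52 used all the named pain scores and assumed EQ VAS to 3-month pain correlations of −0.24 to −0.5. Leaving out the health and opioid variables gave biases of 0.03 to 0.28 points where they mattered. Adding only 1-month EQ VAS and OMED removed these, and raised root mean squared error by at most about 0.03 points where they were not needed. Adding four EQ VAS and two OMED variables cost slightly more precision for no further gain.

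**6. Could it reverse the test?** Take 35 observed subjects with mean change −2 and SD 3.5 across all 52, ignoring the extra imputation variance. The mean needed for significance is t(0.975, 51) × 3.5/√52 = 0.974 in absolute value. The 17 missing would need a mean change of (−0.974 × 52 + 2 × 35)/17 = +1.1, a shift of 3.1 points. The largest shift in imputed values in step 3 is 1.26.

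**The case against.** The strongest reply has four parts.

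- **Direction is unproven.** A reader might infer that imputed pain is biased toward improvement. The documents give no association between health and later pain, the plan assumes none with missingness, and the bias is zero or reversed in some scenarios, for instance if sicker patients report less pain on more opioid. This stands: the bias is a possibility, not a finding.
- **The model is not blind to decline.** It contains three post-ablation pain scores, which carry some health information. In one check, using all the named pain scores instead of 1-month pain alone cut the bias from 0.14 to 0.11. This stands, but the scores do not carry all of it.
- **The model is not fixed.** The SAP list is permissive, CIP 13.1.4 allows other imputation strategies, and both documents promise to examine the reasons for and timing of missing data. So it is wrong to say the plan rules these variables out. However, EQ VAS and OMED are not among the variables named, and discretion over which listed ones to use is itself a reason to prespecify.
- **The near-perfect correction is built in.** Step 3 generated missingness from the health score alone and observed that score in everyone. In the trial, a subject too ill for the 1-month visit may lack pain and EQ VAS together. This stands: the simulation shows what omission can cost, not that the fix removes all bias.

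It is also true that this is a sensitivity analysis. In the scenarios with positive partial correlation, the completers analysis is the more biased of the two.

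**Conclusion.** The point holds in a limited form. The imputation model omits post-ablation health and opioid dose, both collected, while the plan names deteriorating health as a main cause of loss. If 1-month health predicts missingness, and predicts higher 3-month pain beyond the early pain scores, the sensitivity analysis would overstate improvement by about 0 to 0.3 points. The upper end is 0.3/2 = 15% of the 2-point minimal clinically important difference. That range rests on assumed correlations and odds ratios, and the true bias could be nil or of opposite sign.

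A reader might infer that the primary conclusion is at risk. The calculation does not support that: at the design effect the missing subjects' mean would have to shift by about 3.1 points. What suffers is the estimate and the reassurance drawn from the check. This is a worthwhile, inexpensive improvement, not a flaw that invalidates the plan.

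**What to change.** In SAP 7.9.1, replace the permissive introduction with a fixed list: worst pain at baseline, 3 days, 1 week, 1 month and 3 months; age; baseline Karnofsky; and, as auxiliary variables, 1-month EQ VAS and 1-month OMED. Drop time from diagnosis from the start, since only the year is collected. Then no variable has to be removed in response to non-convergence, and the final model does not depend on the data. Leave the rest of the procedure unchanged.

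The cost is one revised SAP passage and no new data. The model goes from 8 variables to 8 − 1 + 2 = 9 in about 52 subjects, with a small loss of precision if the additions prove uninformative. The change does not settle what a 3-month score means for subjects who died, and it does not help those who also missed the 1-month visit.

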### 9.8. Assessment of Safety

Subjects will be assessed for potential reportable adverse events and device deficiencies (as defined in Section 11) at each study visit.

#### 9.9. Recording Data

The Investigator must ensure accuracy, completeness and timeliness of the data reported in the eCRFs and in all other required reports. Data reported on the eCRFs must be consistent with the source documents, and discrepancies need to be justified in a documented rationale, signed and dated by the Investigator, and filed in the subject medical file or appropriate location.

#MDT16075 Version 4.0 Page 40 of 81

All source data entered in the eCRFs should be located in the subject's medical records/source document (electronic or paper), (e.g., hospital records, surgery reports, x-rays, MRIs, CTs, or any other material that contains original information used for data collection including the documentation of AEs and study source document completed by the Investigator or site staff). Subject completed questionnaires as well as data collected during subject phone calls will be considered as source data.

This study will be conducted using a remote data capture system. The Oracle Clinical Remote Data Capture (RDC) system allows the study centers to enter study data into the sponsor's database over a secure internet connection. Required data will be taken from source documents and directly entered into the study database by authorized site personnel in accordance with applicable regulations.

If the subject is unable to return to the investigational site for their scheduled clinic visit, the study site can contact the subject and collect the following data by phone using the phone visit source document worksheet:

- BPI conducted by phone
- EQ-5D-5L phone version
- Oral narcotic intake in the past 24 hours
- Concomitant procedures/treatments
- Reportable adverse events and/or device deficiencies

The Principal or Sub-Investigator, or an individual delegated by the Principal Investigator on the Delegation of Authority and Signature Form, is responsible for documenting and entering data for the study on the eCRFs. The Principal Investigator or delegated Sub-Investigator is required to approve all data on CRFs via electronic signature.

# 9.10. Deviation Handling

Protocol deviations are digressions from the written protocol defined as an event where the clinical investigator or site personnel did not conduct protocol-required procedures according to the study protocol. Protocol deviations are to be preapproved by Medtronic study personnel and the IRB/EC (as required) unless the deviation is necessary to protect the health, safety, or welfare of a subject in an emergency situation. The investigator or delegated site personnel should immediately contact the designated Medtronic study personnel to discuss the impact of the potential deviation; prior approval of deviations should be documented. Prior approval is generally not required if the deviation is due to an emergency circumstance or an unforeseen circumstance that is beyond the investigator's control; however, these deviations should be reported to Medtronic and the IRB/EC (as required) after site personnel become aware of the deviation. All protocol deviations must be reported on the Protocol Deviation eCRF after the site's awareness of the deviation.

The sponsor may choose to terminate the study at a site for failure to follow the written protocol and investigator agreement. If this occurs, the Investigator and IRB/EC will be notified in writing of the reasons for the termination.

#MDT16075 Version 4.0

Page 41 of 81

### 9.11. Subject Withdrawal or Discontinuation

Subjects are free to voluntarily withdraw from the study at any time and for any reason. The investigator can withdraw a subject from the study at any time and for any reason. Withdrawn or exited subjects will be followed under normal medical practice.

Examples of reasons for subject discontinuation include, but are not limited to, those listed below:

- If the subject does not meet all eligibility criteria
- Subject death
- Subject lost to follow-up
- Subject voluntarily withdraws from the study
- Subject becomes pregnant
- OsteoCool RF ablation was not performed or was aborted and RF therapy was not delivered
- Investigator terminates the subject's participation in the study (e.g., failure to return for scheduled visits, failure to comply with the protocol)
- Any clinical laboratory abnormality, inter-current illness, or other medical condition or situation
  occurs such that continued study participation would not be in the best interest of the subject-
- Normal study completion. After the completion of the 12 Month follow-up visit, a Study Exit eCRF should be completed to document normal study completion.
- Sponsor terminates study early due to low enrollments and/or attrition

Study Exit eCRF must be completed on all enrolled subjects. Detailed notes as to why the subject was withdrawn from the study (e.g., discomfort, lack of efficacy, questionnaires too burdensome, lost to follow-up, death) should be included. There will be no further medical care provided under the study after a subject exits.

If the RF ablation was not performed, aborted or RF therapy was not delivered, the subject will be discontinued from the study and a Study Exit eCRF should be completed. Withdrawn subjects will not be replaced.

When a subject is withdrawn from the study between scheduled visits, complete the unscheduled visit eCRF (with the exception of lost to follow-up and death) as well as the Study Exit eCRF.

Prior to deeming a subject is lost to follow-up, telephone calls must be documented in the subject's medical record. If a minimum of three attempts to contact the subject have failed (e.g. phone and mailed letter), and no response is received, the site should exit the subject and complete the Study Exit eCRF.

If early termination is due to death related to the device, procedure and/or therapy related adverse event, the Adverse Event eCRF should be completed as well as the Study Exit eCRF. In case of death, the Investigator should maintain original source documents pertaining to the death of any subject (e.g., death certificate; autopsy report, if done; hospital death summary if subject died in hospital, if available).

#MDT16075 Version 4.0

Page 42 of 81

Medtronic

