#### **Baseline**

Verify eligibility criteria, obtain pregnancy test
collect demographic, cancer history, baseline images at the target
site(s) if available, Karnofsy Performance Scale (not for benign bone
tumors), concomitant medications/treatments, BPI, EQ-5D-5L,
EORTC-QLQ-C15-PAL (not for benign bone tumors), reportable adverse
events/device deficiencies and deviations

≤21 days after baseline visit Enrollment, Baseline and RF ablation can occur on the same day

# OsteoCool Procedure Day 0

Collect RF ablation procedure and OsteoCool details, reportable adverse events/device deficiencies, deviations, concomitant medications/treatments, and Generator data uploads

Study Discontinuation No

Was the RF therapy delivered?

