#### 6.1. Duration

The start of the study for each subject is defined as the date the subject first signs the informed consent. Enrolled subjects who do not meet baseline eligibility or who do not undergo the OsteoCool procedure will be exited from the study (e.g. RF therapy was not delivered). The completion of the study for each subject is defined as the conclusion of the 12 Month Visit (Study Exit). Each subject's participation in the study is expected to last approximately 1 year from the date of the OsteoCool procedure. Each subject will be evaluated prior to the OsteoCool procedure, during the procedure, prior to hospital discharge, 3 days, 1 week, 1-, 3-, 6-, and 12-months post procedure.

The estimated time needed to enroll all subjects is approximately 3 years. The overall study duration, from first subject enrollment to last subject visit, is expected to last approximately 5 years. The completion of the study is defined as the approval of the Final Study Report and closure of all sites.

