**Table 7-1: General Equipment** 

Products	Model/type	Product Description
OsteoCool™ RF Generator	OC01	Is a coaxial, bipolar RF Ablation platform. It is non-sterile and reusable. RF energy is applied to the subject according to the selected or configured settings. The procedure is automatically monitored, on a per-channel basis, for unexpected responses, which will cause messages to be displayed and RF energy delivery cessation, if appropriate.
OsteoCool™ Cart	OCA01	Is a non-sterile, reusable cart to mount the OsteoCool™ Radiofrequency Generator and OsteoCool™ Peristaltic Pump
OsteoCool™ Desk Stand	OCA02	Is a non-sterile, reusable desk stand to mount the OsteoCool™ Radiofrequency Generator and OsteoCool™ Peristaltic Pump
OsteoCool™ RF Pump Unit and Cable	OC02 – (OC02-R - replacement part only)	Is a non-sterile, reusable pump that circulates sterile water through a closed-loop system during OsteoCool™ radiofrequency (RF) ablation procedures. The OsteoCool™ Peristaltic Pump is suitable for continuous operation.
OsteoCool™ Connector Hub	OC04	Is a non-sterile, reusable cable which provides a path for delivery of radiofrequency (RF) energy and temperature signals to/from OsteoCool™ RF Ablation Probes, OsteoCool™ Independent Thermocouple Monitor, and OsteoCool™ RF Generator.

#MDT16075 Version 4.0 Page 27 of 81

OsteoCool ™ Power	OCE-NEMA515	
Cord North		
America		
OsteoCool ™ Power	OC-CE12350	
Cord Italy		Is the Power Cord for the OsteoCool Radiofrequency
OsteoCool ™Power	OC-BS363	Generator
Cord UK		
OsteoCool ™Power	OC-SEV1011	
Cord Swiss		
OsteoCool ™Power	OCE-CEE7-INT	
Cord Europe		

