#### **Analysis Populations**

There are 3 analysis populations:

The *Enrolled* will include all enrolled subjects and will be used in the safety measures.

The populations of study subjects to be included in the efficacy analyses (primary objective, secondary objective, and additional measures) are described below.

**Treated:** The Treated population will be defined as all subjects who are successfully treated with the OsteoCool™ RF Ablation system. This is similar to a Full Analysis Set.

**Completers:** The Completers population will be defined as the subset of **Treated** subjects who provided endpoint data at the 3-Month Visit. The Completers population will be a subset of the Treated population. The Completers population will be the analysis population for the primary objective hypothesis testing.

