### 7.1.3 Analysis Sets

#### **Analysis Sets**

There are 3 analysis sets:

**Enrolled**: all enrolled subjects. The demographics of this set, and specifically the subjects in this set but not in the Treated Analysis set, will only briefly be characterized. Otherwise, the efficacy and safety analyses will be on the following two analysis sets.

The analysis sets to be included in the efficacy analyses (primary objective, secondary objective, and additional measures) are described below.

**Treated Analysis Set**: all subjects who are successfully treated with the OsteoCool™ RF Ablation system.

**Completers Analysis Set**: the subset of Treated Analysis Set subjects who provided endpoint data at the 3-Month Visit. The Completers Analysis Set will be a subset of the Treated Analysis Set. The Completers Analysis Set will be the analysis population for the primary objective hypothesis testing.

The safety analyses will utilize the Treated Analysis Set.

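### CIP 9.11 is inconsistent on whether a subject whose ablation is aborted after some RF delivery leaves the study, and the Treated set is limited to successfully treated subjects with no criterion for success

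*Combined protocol and SAP*

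**What the plan says.** **Study exit.** CIP 9.11 states the exit condition twice. The list of reasons for discontinuation has: "OsteoCool RF ablation was not performed or was aborted and RF therapy was not delivered". That list is introduced by "Examples of reasons for subject discontinuation include, but are not limited to, those listed below". A later paragraph of the section is a directive: "If the RF ablation was not performed, aborted or RF therapy was not delivered, the subject will be discontinued from the study".

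Four other places address the same decision:
- Figure 6-1, repeated as SAP Figure 5-1, has a single decision node after the procedure: "Was the RF therapy delivered".
- CIP 6.1 and SAP 5 say that enrolled subjects "who do not undergo the OsteoCool procedure will be exited from the study (e.g. RF therapy was not delivered").
- CIP 8.2 uses the same criterion of not undergoing the procedure, with non-delivery of RF as its example.

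None of these four mentions an aborted procedure.

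**Analysis sets.** In CIP 13.1.4, "The Treated population will be defined as all subjects who are successfully treated with the" OsteoCool system. SAP 7.1.3 has the same condition: "all subjects who are successfully treated with the" system. Neither document defines success. Completers, the set for the primary test, is a subset of Treated. The multiple imputation and last-observation-carried-forward analyses both run on Treated. For safety, the CIP uses all Enrolled subjects, while SAP 7.1.3 and 7.10 use Treated.

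**The concern.** Consider a subject whose ablation is stopped part-way, after some RF energy has been given. The plan does not handle this subject consistently.

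If a site follows the directive in 9.11, the subject leaves on Day 0. CIP 11.2 collects adverse events through subject discontinuation and follows open events no further than that, so later related events would not be captured. The safety measure is all related events up to the 12-Month Visit. A site guided by Figure 6-1 would keep the same subject for a year, so the data would not be comparable across sites.

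The undefined word *successfully* raises a second question, about selection. If it is applied as an entry condition, membership of the efficacy sets depends on how the procedure went. No planned efficacy analysis would bring the excluded subjects back, because the sensitivity analyses start from the same set. In an open, single-arm study analysed by the sponsor's statisticians or designees, that judgement could be made after outcomes are known.

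**Working it through.** **1. The exit passages side by side, for a procedure aborted after some RF was delivered.**

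| Place | Condition for exit | Result for this subject |
|---|---|---|
| CIP 9.11, directive | not performed, or aborted, or RF not delivered | exits |
| CIP 9.11, example list | not performed, or aborted with RF not delivered | no listed reason to exit |
| Figure 6-1 / SAP Figure 5-1 | RF not delivered | stays |
| CIP 6.1, CIP 8.2, SAP 5 | procedure not undergone (example: RF not delivered) | no stated reason to exit |

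The directive is the outlier, but it is also the sentence worded as an instruction.

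**2. Can the case arise?** Table 7-1 says the generator monitors for "unexpected responses, which will cause messages to be displayed and RF energy delivery cessation, if appropriate". The CIP 10.2.1 warnings also tell operators to discontinue use when temperature readings are erratic. Neither passage says that the procedure is then abandoned rather than resumed. Interruption is foreseen, but its frequency is not given.

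**3. The plan's own sample size.** The inputs in CIP 13.3.5 are mean change 2, SD 3.5, two-sided alpha 0.05, power 0.90 and 32% loss. From the noncentral t distribution, n = 34 gives power 0.899 and n = 35 gives 0.907, so 35 is right. 35/0.68 = 51.5, so 52 treated. Both figures reproduce and do not depend on this point.

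**4. Illustration of size (assumed inputs).** Suppose 2-10% of 52 procedures are partial deliveries: 0.02 × 52 = 1.0 to 0.10 × 52 = 5.2 subjects. At the plan's 68% completion, 0.7 to 3.5 of them would have 3-month data. Take 35 completers with mean -2.0 and SD 3.5, and add k subjects with mean change 0.

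- k = 0: t = -2.0/(3.5/√35) = -3.38, p = 0.0018.
- k = 3: mean = (35 × -2.0 + 3 × 0)/38 = -1.84.
  - All three exactly zero: the squared changes sum to 34 × 3.5² + 35 × 2² = 556.5. Pooled SD = √[(556.5 - 38 × 1.842²)/37] = 3.40, t = -3.34, p = 0.0019.
  - The three spread about zero with SD 3.5 (adding 3 × 12.25 = 36.75 to the sum): SD = 3.54, t = -3.21, p = 0.0028.
- k = 5: mean = -70/40 = -1.75. With the same spread, t = -3.11, p = 0.0035.

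Three subjects with data imply about 3/0.68 = 4.4 partial deliveries, so k = 3 is already near the top of the assumed range and k = 5 lies beyond it.

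**5. Power if n stays at 35 and a share f of those analysed are partial deliveries with mean change 0.** Mean = 2(1 - f); variance = 3.5² + 4f(1 - f). Power is 0.894 (f = 2%), 0.872 (5%) and 0.830 (10%), against 0.907 with none. These figures assume that partial delivery brings no benefit and that partial deliveries provide 3-month data as often as other subjects.

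**The case against.** **On the exit rule.** A reader might infer that 9.11 contains two opposite rules of equal standing. The text does not go that far. The narrower wording sits in a list of examples that is expressly not exhaustive, so it never says that other subjects stay. The section also lets the investigator withdraw anyone at any time. What stands is one mandatory sentence that does not fit a delivery-based rule found everywhere else.

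**On the Treated set.** A reader might also infer that partial deliveries, or subjects with one of two target sites completed, are excluded by design. The documents point the other way:
- CIP 13.1.4 likens Treated to a full analysis set.
- SAP 7.1.3 (Objective Cohorts) describes those without a cohort as subjects who do not undergo the procedure.
- SAP 7.7 tabulates technical success by site, which would be largely redundant if success were an entry condition.
- SAP 7.10 justifies using Treated for safety on the ground that only subjects not receiving RF ablation are left out.

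The intended meaning is therefore probably everyone who received RF ablation. None of this text defines the term, though, so the literal reading remains open.

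**On transparency and size.** Disposition and reasons for discontinuation are reported by visit, enrolled subjects who are not in Treated are briefly characterised, and all device deficiencies are collected. Early exits would be visible, although not analysed for efficacy. Nothing in the documents shows that partly treated subjects do worse. The illustration assumes it, and even so the test against zero barely moves.

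**Conclusion.** The point holds as an inconsistency in the exit rule together with an undefined entry condition for the main analysis set. The clearest consequence is for safety. Under the directive, a partly treated subject leaves on Day 0 and event collection ends. Under a literal reading of Treated, the same subject would also be missing from the SAP safety tables, whose stated rationale covers only people who received no RF ablation.

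For efficacy, exclusion is possible but not established. It would be wrong to conclude that the primary result is biased or that the primary test is at risk. No abort rate is given, so no bias can be computed. If three zero-change subjects are assumed, the mean shifts by 0.16 points (from -2.0 to -1.84) and p stays below 0.003. The sample size of 35 completers and 52 treated stands. The case for acting is that the ambiguity is cheap to remove and should be settled before outcomes are known.

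**What to change.** 1. Reconcile the directive in CIP 9.11 with the list in that section, Figure 6-1 (and SAP Figure 5-1), CIP 6.1 and 8.2, and SAP 5, so that one study-exit rule applies at all sites and states what happens after an aborted procedure with some RF delivered. Which rule to adopt is for the sponsor and investigators to decide.
2. In CIP 13.1.4 and SAP 7.1.3, replace the success condition with a delivery-based definition: all subjects in whom any RF energy was delivered by the system. This matches the Figure 6-1 decision node and the reasoning in SAP 7.10.
3. Keep technical success in SAP 7.7 as a descriptor, and say that it does not determine set membership.

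The cost is a sentence or so in each place, with no new visits or procedures. A few more subjects may enter the analysis sets, the mean change may be slightly less favourable, and power at 35 completers may be somewhat below 0.907 if partial deliveries turn out to be common.
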